7 SAFETY AND ADVERSE EVENTS

Loss of confidentiality is unlikely but possible. The breach of confidentiality could result in disclosure of HIV status.

During the OGTT procedure, there is a risk of a bruise, slight pain, inflammation of the vein, bleeding at the site of puncture and fainting. There is also the rare possibility of infection. Only an experienced, registered nurse will draw blood; so the likelihood that these problems will occur is low. The cleansing of the site prior to puncture and the maintenance of sterile techniques will minimize the risk of infection. There will be some discomfort when the tube is placed in the arm. Participants will also be at risk of developing hypoglycemia (low blood sugar) which may cause light headedness, sweating, shakiness, and dizziness. Severe low blood sugar can cause seizures and/or coma. These problems are very rare and we prevent them by

close monitoring of participant's blood sugar level.

Venipuncture for blood draw will be performed 2x (baseline and week 12). There is some risk for bruising or discomfort during venipuncture. Risk of minor bruising is observed at an approximate rate of 12% and larger, more extensive bruising occurred at approximately 3% of all venipunctures. Bruising is anticipated to be minimal and resolve without intervention.

Mild discomfort associated with venipuncture is a normative experience as this requires a small puncture of the skin; however, the discomfort is minimal and very short in duration (< 5 seconds). No long-term effects anticipated as a result of the mild discomfort of venipuncture performed by a licensed registered nurse.

Hypoglycemia incidence during OGTT is approximately 6%. Severity is likely to be minimal as these participants will be monitored by a registered nurse during the entire OGTT. Registered nurses are trained to recognize signs/symptoms of hypoglycemia and to respond appropriately. Effects of hypoglycemia are immediately reversible with administration of oral glucose in a conscious patient. MD consultation is available.

Mild psychological discomfort may occur during completion of cognitive battery and/depression scale; however, the discomfort would be short in duration (30 minutes – 1 hour). Prevalence of test anxiety is believed to be higher in older versus younger adults and may be due to concerns over cognitive decline;

5

6 although prevalence is unknown. Nonetheless, even in those individuals with testing anxiety, the effects are

short in duration. In addition, there are no known lasting testing anxiety effects in older populations.

Diet: Those randomized to the KD may experience normal transient reactions such as hunger, weakness, lightheadedness, constipation, fatigue, dizziness, or cravings for certain foods during the first few days of the

KD; however, these effects are mild in nature and resolve without intervention as the body adapts to the new diet. No known long-term risks associated with KD. The most common adverse effects are constipation

(prevalence ~30%), loss of energy (prevalence ~35-37% and bad breath (prevalence ~ 43%), all of which resolve within few weeks as the body adapts to the new diet. Daily energy intake eucaloric (weight maintaining) so changes in weight not anticipated.

Inquiry regarding adverse effects assessed by project coordinator at week 4, week 8, and week 12. Study physician notified immediately for serious adverse effect. In addition, documentation submitted to the IRB

submitted within three business days after any adverse effect reported. Medical monitoring conducted by

primary investigator in collaboration with the study physician. Monitoring completed by registered nurses

during data collection in the Clinical Research Unit.

All testing will be performed by trained personnel, blood samples will be collected by registered nurses, and all equipment will be calibrated daily before testing. Prior to giving consent, all potential participants will be allowed to see equipment and facilities. If an individual indicates discomfort or the desire to discontinue testing, tests will be terminated immediately.

During routine visits and telephone calls, the study coordinator will query participants for any adverse events since their last contact with study personnel. In the case of an adverse event during times of testing, a study physician will be on call. A medical doctor will provide medical supervision for this study. All adverse events will be reported to the UAB IRB and reviewed by the investigative team. Should any of these individuals and/or the IRB identify that any adverse event may be related to the study protocol, testing will be suspended and the protocol will be amended accordingly.

Transient testing fatigue is likely to occur by the end of data collection on weeks 1 and 12; however, the fatigue will be minimized by the provision of a 45-minute break and a meal following the OGGT.

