4. SUBJECT SELECTION

4.1

4.2

4.3

INCLUSION CRITERIA

> 50 years with stable HIV and cognitive impairment as determined by the Modified Telephone Interview for Cognitive Status (TICS-M) Scale. Participants required to have stable HIV infection as evidenced by CD4+ lymphocyte count > 350 cells/mm³ for at least two years and prescribed their current cART regimen for at least six months.

EXCLUSION CRITERIA

Current drug or alcohol abuse (> 3 drinks/day), past medical history of mental disorders (i.e., schizophrenia, bipolar), neural injury (i.e., cerebral vascular accident or traumatic brain injury), dementia, Parkinson's, diabetes mellitus, hearing impaired, or any other condition that contraindicates participation.

SUBJECT RECRUITMENT AND SCREENING

Participants recruited from the UAB 1917 HIV/AIDS Clinic using fliers within the clinic as well as by advertisement on a rolling kiosk located in the clinic lobby.

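### No adverse-effect inquiry is dated before week 4, although Section 7 expects ketogenic diet reactions in the first few days, so early effects may be under-counted through recall

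*Combined protocol and SAP*

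**What the plan says.** Section 7 (Safety and Adverse Events) makes two statements about when participants are asked. The first gives dates: "Inquiry regarding adverse effects assessed by project coordinator at week 4, week 8, and week 12". The second gives none: "During routine visits and telephone calls, the study coordinator will query participants for any adverse events since their last contact with study personnel".

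The same section describes the timing of the effects. Among the transient reactions to the KD are "lightheadedness, constipation, fatigue, dizziness, or cravings for certain foods during the first few days of the" diet. For the most common effects it gives rates, constipation first: "prevalence ~30%), loss of energy (prevalence ~35-37% and bad breath (prevalence ~ 43%), all of which resolve within few weeks".

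Section 5 (Study Procedures) starts meal delivery in week 1, the week after baseline. It dates data collection at baseline and week 12, with cognitive testing also at week 18, and plans 7 participants per arm. Section 4 (Subject Selection) enrols people "> 50 years with stable HIV and cognitive impairment as determined by the Modified Telephone Interview for Cognitive Status (TICS-M) Scale". No diary, symptom checklist, or recording of onset and resolution dates is described.

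**The concern.** On Section 7's own account, the dated inquiries begin after the expected onset of the reactions and possibly after many have resolved. If nobody calls earlier, a week-4 question about week 1 depends on memory. Mild symptoms that have passed are the easiest to forget, and their onset, duration and severity are harder to recover than the fact that they occurred. The participants are selected for cognitive impairment.

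Section 1.3 describes this as, to the investigators' knowledge, the first study of a KD in people with HIV, so a fair record of early effects has value for whatever follows. Someone who stops the diet before week 4 might never be asked why. In an arm of 7, one such person is 1/7, or about 14% of the arm. The reporting steps in Section 7 also begin only once study staff know of an event.

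**Working it through.** **Timeline, from Sections 5 and 7**

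| Time | What the plan provides |
|---|---|
| Baseline | Clinic data collection |
| Week 1 | Meals begin; reactions expected in the first few days |
| Weeks 1 to 4 | No dated visit, call or inquiry; common effects resolving over a few weeks |
| Weeks 4, 8, 12 | Dated adverse-effect inquiries |
| Week 18 | Cognitive visit; no dated inquiry |
| Undated | Query at routine visits and telephone calls, back to last contact |

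Read as written, the plan guarantees no inquiry in the window where onset is expected. An earlier call is allowed for but not required. Without one, recall of a week-1 event at week 4 spans roughly three to four weeks.

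**Is there a stated figure to reproduce?** No. The documents give no precision or detection figure for adverse events, so what follows is illustration only.

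**Inputs.** The KD arm is n = 7 (Section 5). The rates p are 0.30 for constipation, 0.35-0.37 for loss of energy and 0.43 for bad breath (Section 7). The recall fraction r is an assumption, because the documents give none.

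**Expected cases, n × p**
- Constipation: 7 × 0.30 = 2.1
- Loss of energy: 7 × 0.35 to 7 × 0.37 = 2.45 to 2.59
- Bad breath: 7 × 0.43 = 3.01

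**Chance of recording at least one constipation case, 1 − (1 − 0.30r)^7**, taking every case as resolved by week 4 and therefore dependent on recall:

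| r (assumed) | Expected recorded, 2.1 × r | Chance of at least one |
|---|---|---|
| 1.0 | 2.10 | 1 − 0.70^7 = 0.918 |
| 0.7 | 1.47 | 1 − 0.79^7 = 0.808 |
| 0.5 | 1.05 | 1 − 0.85^7 = 0.679 |
| 0.3 | 0.63 | 1 − 0.91^7 = 0.483 |

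The whole spread comes from r. If some cases are still present at week 4, the loss is smaller than the table shows.

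**The case against.** A reader might infer that the plan will miss the early reactions. The documents do not support that, for these reasons:

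- The undated query asks about "any" event back to the last contact, so an effect that began and ended before week 4 is still asked about.
- Telephone calls are expressly foreseen, and one could fall in week 1 or 2. An unscheduled call is not the same as no call.
- Section 7 says the common effects "resolve within few weeks as the body adapts to the new diet", so some may still be present at week 4.

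All three points stand. They reduce the claim to possible under-counting through recall. They do not remove it, because nothing in the plan fixes an early contact. The nutritional counselling in Section 5 might provide one, but it is undated and described only for the KD arm.

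It might also be inferred that tolerability is a main result that would be biased. Section 2 lists feasibility of recruitment, retention and adherence, and Section 6 plans no adverse-event analysis. Even the direction of any net bias is not certain: the trial is unblinded (Section 3), and expectation could raise KD reporting while recall lowers it.

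Other counterweights also stand. Section 4 excludes dementia. Section 7 describes the transient reactions as mild and self-resolving, and has the study physician told at once of serious effects. On its face the routine-visit query covers week 18, so that point needs only a clarifying sentence.

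**Conclusion.** The concern holds in a limited form. The only dated inquiries come after the period in which Section 7 expects the reactions to start, and no earlier contact is scheduled. Early KD effects may therefore be under-counted, and their timing and severity poorly recorded.

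The documents do not allow the loss to be sized. It is nil at full recall. Under assumed recall of 30-70%, with all cases resolved by week 4, the chance of recording any constipation among 7 KD participants is 48-81% rather than 92%. Neither assumption can be checked from the documents.

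This is an inexpensive improvement to safety capture. No planned outcome or analysis is invalidated by leaving the schedule as it is.

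**What to change.** - Keep the inquiries at weeks 4, 8 and 12.
- Add scheduled coordinator telephone inquiries in the first week of meals and at about week 2, with the same script and timing in both arms.
- Use a fixed checklist of the reactions Section 7 already lists, and record onset and end dates.
- State that the routine-visit query also applies at week 18.

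The direct cost is at most 2 × 14 = 28 short calls by the existing coordinator, plus a few minutes at a visit already planned.

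The main downside is reporting. At Section 7's rates, taking 36% for loss of energy, about 2.1 + 2.5 + 3.0 = 7.6 instances of the three common effects are expected in the KD arm, counting a participant with two effects twice. A checklist would bring more of them to light. Section 7 calls for documentation to the IRB within three business days of any reported adverse effect, and says testing is suspended and the protocol amended if an event may be related to the study protocol. Read literally, that sits awkwardly beside a list of mild reactions the same section expects from the diet. The two statements must be reconciled before active solicitation begins; how to do so is for the investigator and the IRB.

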5 STUDY PROCEDURES

Following IRB approval and informed consent, eligible participants randomized to either the experimental ($n = 7$) or control group ($n = 7$) and scheduled for baseline data collection. Laboratory, demographic, and anthropometric assessments were completed UAB's Clinical Research Unit (CRU). Baseline data: demographic questionnaire, oral glucose tolerance test (OGTT), inflammatory assays and lipid panel as well as an anthropometric evaluation. Even though all snacks and meals for the KD group provided, KD group participants also provided nutritional counseling specific to the KD as well as provided with handouts. Food selected from an 8-day menu. Meals matched for energy content to maintain current energy balance (eucaloric) consisting of < 50 grams CHO/day. Daily CHO intake primarily derived from fresh vegetables.

After laboratory assay and body composition assessments collected, questionnaires and cognitive testing in a private conference room away from outside distractions completed. Delivery of meals/snacks (week 1) to begin the week following baseline data collection.

Food delivery via courier on the same day of the week across the study. All frozen/refrigerated items delivered in a commercial grade cooler. All items clearly labeled with easy-to-understand preparation instructions.

Data Collection

Data collection in the UAB Clinical Research Unit after a 12-hour fast collected by registered nurses well-versed in research methodology. Data collection described below. **Data collection collected at baseline**

and week 12 unless otherwise stated. **NOTE: Cognitive assessments completed at baseline, week 12, and week 18.**

Demographics (baseline only): Age, education, gender, marital/partner status, employment status/disability eligibility, SES (Medicaid, food stamps, public housing eligibility), years since HIV diagnosis (baseline only).

[figure not shown]
Anthropometrics: Height, weight, BMI, waist and hip circumference (baseline/week 12). Height (nearest 0.1 cm), waist circumference (nearest 0.1 cm), and hip circumference (nearest 0.1 cm) measured with Gulick tape measure. Weight (nearest .01 kg) assessed using a Tanita body composition analyzer BC418, Tanita Corp of America, Arlington Heights, IL. BMI calculated.²³ Waist circumference measured at the umbilicus at end of inspiration. Hip measures evaluated at widest hip portion.

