Oral Glucose Tolerance Test (OGTT): 75 g at baseline (time 0). At ~7 am, after a 12-h fast, a flexible intravenous catheter will be placed in an antecubital space. Blood samples will be collected at times 0, 10, 20, 30, 60, 90, and 120 minutes. OGTT performed at baseline. Fasting glucose, insulin, and c-peptide to be assessed at week 12.

Lipids: Total, high density cholesterol (HDL) and triglycerides were measured using SIRRUS analyzer and low density lipoprotein were calculated using the method of Friedewald.³⁰

Inflammation Markers: Assessed by immunoassay in fasting morning sera before and after the intervention. High-sensitivity C-reactive protein (CRP), TNF- α and IFN γ , IL-1B, IL-6, IL-8, and IL-12p70

Cognitive Battery Domain

Cognitive Measures

[figure not shown]

[figure not shown]
Speed of Processing

WAIS-III Digit Symbol measures visuospatial tracking, attention, and speed of processing. Participants are presented with a key which has numbers paired with a unique symbol. They are given rows of numbers with blank spaces underneath them. The task is to use the key to fill in the blank spaces with the symbol that corresponds to that number. Scores are calculated by the number of squares filled in correctly.

WAIS-III Symbol Search is similar to the Digit Symbol Test. Participants are given rows of symbols and must use the key to write the corresponding number (1-9) in the blank under the symbol.

Trails Making Test A – This measure of motor speed and speed of processing is very reliable ($r = 0.80 - 0.90$) Twenty-five circles numbered 1 to 25 are located randomly on the page. Participants instructed to connect the dots sequentially (1-2-3-4). The score is determined by the time to complete.

[figure not shown]

Attention

WAIS-III
Digit Span – A measure of attention and concentration. Participants must recall blocks of sequenced numbers (1 through 9) presented to them; the length of the blocks are small at first and slowly build making it more difficult to attend. Digits are to be immediately recalled forward (e.g., 1..2..3) and backward (e.g., 3..2..1).

[figure not shown]

Verbal

[figure not shown]
Hopkins

Verbal Learning Test-Revised (HVLTR) Trials 1-3 – A test of verbal recall and consists of 12 words, four

[figure not shown]

from each of three semantic categories. The total recall is used in analyses, but true-positive recognitions and false-positive errors can be used.

**Learning/
Memory**

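### Does a safety remark implying a week-12 glucose tolerance test put the week-12 outcomes in doubt?

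*Combined protocol and SAP*

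**What the plan says.** Section 5 lists the OGTT among the baseline assessments. Its OGTT paragraph then separates the two visits: "OGTT performed at baseline. Fasting glucose, insulin, and c-peptide to be assessed at week 12". The sampling scheme is also given there: "Blood samples will be collected at times 0, 10, 20, 30, 60, 90, and 120 minutes". The general rule in Section 5 is collection at baseline and week 12 unless the text says otherwise, and for the OGTT it does.

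On the order of the visit, the baseline paragraph of Section 5 has "After laboratory assay and body composition assessments collected, questionnaires and cognitive testing in a private conference room". Cognition is measured three times: "Cognitive assessments completed at baseline, week 12, and week 18". The ketogenic meals are described as "consisting of < 50 grams CHO/day", and the diet starts after the baseline visit: "Delivery of meals/snacks (week 1) to begin the week following baseline data collection".

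Section 7, in a closing remark on testing fatigue, speaks of the visits thus: "on weeks 1 and 12; however, the fatigue will be minimized by the provision of a 45-minute break and a meal following the OGGT" (OGGT is taken to mean the OGTT). Earlier in the same section the risks of the OGTT are described. Venipuncture is then listed as a separate item, done twice, at baseline and week 12.

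Section 6 (Statistical Plan) names the OGTT only in the baseline descriptive summary. Its primary analysis is an ANCOVA of change from baseline, applied to the impairment score, the inflammatory markers and the cardiometabolic factors. The last group is not itemised there.

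**The concern.** Read plainly, the Section 7 remark puts an OGTT in the week-12 visit, and Section 5 does not. The two readings would give different data. With no week-12 test, post-load glucose has no change score, although cardiometabolic profile at 12 weeks is listed under the primary objective. With a week-12 test, such change scores exist but no summary of the curve is named.

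The second reading could also touch cognition. Section 1.1 explains that ketones arise when carbohydrate is not available. If ketogenic participants drank a 75 g load shortly before the week-12 battery, they would be tested after more carbohydrate than a whole day of their diet allows, while no limit is stated for the patient-choice group. That difference would be specific to one arm and would arise after baseline, so the baseline covariate could not remove it. The week-12 score is also the starting value and covariate for the 12-to-18-week persistence analysis.

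**Working it through.** The plan gives no statistical figure to reproduce here. The check is a comparison of texts with a little arithmetic.

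**1. What each reading implies for week 12**

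| Item | Section 5 schedule | Section 7 remark read literally |
|---|---|---|
| Glucose load at week 12 | none | 75 g |
| Post-load samples at week 12 | 0 | 6 (the 7 sampling times less time 0) |
| Load against ketogenic daily limit | not applicable | 75 / 50 = 1.5; the limit is below 50 g, so the ratio is above 1.5 |
| Earliest end of break after the load | not applicable | 120 + 45 = 165 minutes |
| Fasting glucose, insulin, C-peptide change | available | available |

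The 165 minutes bears on cognition only if the battery follows the break and if week 12 keeps the order that Section 5 gives in its baseline paragraph. Both are assumptions.

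**2. Which text carries the schedule**

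- Section 5 is the procedural text. It ties the OGTT to baseline in the list of baseline data and twice in the OGTT paragraph, and it names a different set for week 12.
- The separate item in Section 7 for venipuncture at both visits fits a week-12 fasting draw. It does not prove that there was no week-12 OGTT.
- The fatigue remark is loose on another point as well. It places the first collection in week 1, whereas Section 5 makes week 1 the first week of meal delivery, after baseline collection. It can be read as offering the break wherever an OGTT is done.

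**3. What the analysis yields under Section 5**

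Fasting glucose, insulin and C-peptide have both visits: the baseline value comes from the time-0 sample after the overnight fast, and week 12 is stated. Inflammatory markers and lipids have both visits under the general rule. The post-load curve has baseline values only and serves as description, which is the one place where Section 6 names it.

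**4. Does the uneven visit content bias the cognitive contrast?**

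Under Section 5, baseline cognition follows a load and a meal, and week-12 cognition follows a fasting draw with no meal stated. Write the ANCOVA as

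change = a + b × group + c × baseline score + error.

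Suppose the different conditions at week 12 shift every participant's score by d. Then every change shifts by d, and the model becomes

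change = (a + d) + b × group + c × baseline score + error.

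The intercept absorbs d, and the group effect b is unchanged. The raw change within each group moves by d; the comparison between groups does not. At baseline neither group has started the diet, so conditions are alike there too.

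**5. Reach if the literal Section 7 reading were true**

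The week-12 score enters both cognitive ANCOVAs (2 of 2): as the end point of the first, and as starting value and covariate of the second. That shows where an effect would go, not that there is one. The documents give no figure for the effect of a single glucose load on these tests.

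**The case for a change.** The best case for a change is this. Cardiometabolic profile stands under the primary objective, and estimating effect sizes is part of this pilot's stated purpose, so what is measured and under which conditions matters. Section 6 does not resolve the conflict. If its baseline list were carried into the primary analysis, it would call for an OGTT change that Section 5 cannot supply, and it would omit lipids. On the literal Section 7 reading, the arm-specific carbohydrate load is a bias that no covariate in the model can remove.

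Part of this stands. The sentences do not agree, the change variables are not listed, and whether lipids belong among them is for the sponsor to say. But the missing list is a separate question of outcome definition, and it would remain if the fatigue remark were deleted. An analyst would fill it sensibly by analysing change where both visits exist and describing the OGTT at baseline.

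The bias argument needs three things together: a week-12 OGTT contrary to Section 5, the baseline order of testing carried over to week 12, and an effect of one load on test scores. The third has no support in the documents. The mechanisms listed in Section 1.1 include slow ones, such as mitochondrial biogenesis, and the plan itself looks for lasting cognitive effects six weeks after the diet ends. It does not make ketosis on the day of testing a condition of benefit.

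**Conclusion.** The inconsistency is genuine but clerical. It rests on one loosely worded safety sentence against a specific procedural paragraph. Following Section 5 as written gives usable fasting change scores and testing conditions that do not differ by group at each visit, so no wrong result is corrected by a change, and no better method is on offer. In a hypothesis-generating pilot with 7 participants per group, the stake is clarity of wording.

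This conclusion assumes that the trial followed Section 5 and that any shift from the different visit content is the same in both groups. If visit records showed a glucose load before the week-12 battery, that should be reported beside the week-12 cognitive results, and its effect could not be sized from these documents. If the protocol is next edited for other reasons, the Section 7 sentence can be reconciled with Section 5 on the week-12 OGTT and on whether week 1 means the baseline visit.
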